2. The **Movement Disorder Society – Unified Parkinson Disease Rating Scale** (MDS-UPDRS) includes 40 items which are a combination of questions regarding activities of daily living and a physical examination of motor function by the investigator³⁹. This updated UPDRS includes a question about urinary symptoms. A modified Hoehn and Yahr (H&Y) scale is included as part of the MDS-UPDRS. The modified H&Y scale provides a score determined during the physical examination. These instruments will be completed during the *second* clinic visit in order to be performed during a 'defined on' period.
3. The **ICIQ-OAB questionnaire** is a 4-question assessment of OAB symptoms and the degree to which they bother the respondent (urgency, frequency, nocturia, UI)^{32,33}. The ICIQ-OAB questionnaire requires about 5 minutes to complete and will serve as the primary outcome for the study. The participants will complete the ICIQ-OAB-QOL questionnaire⁴⁰ at home, which requires about 20 minutes. The ICIQ questionnaires have been validated in men and women, but not in Parkinson's disease specifically. These questionnaires will be completed at baseline, 6 weeks and 12 weeks.
4. The **UAB Study of Aging Life Space Assessment** will be used to assess individual mobility and need for assistance within the participant's home and community, thus providing a validated assessment of individual independence⁴¹. It is designed to identify the distance through which a person reports moving during the 4 weeks prior to the assessment. Life-Space 0 indicates movement restricted to one's bedroom increasing to Life-Space 5 indicating travel outside of one's town. A score is generated by assigning a value to each Life-Space level based on the frequency of travel to that Life-Space level and degree of independence in getting there. The assessment, which can be performed in less than 5 minutes, leads to a score ranging from 0 ("totally bedbound") to 120 ("traveled out of town every day without assistance").
5. The **MoCA** test is more sensitive to detect mild cognitive impairment than another brief screening measure, the Mini-Mental Status Exam, in PD patients³⁷ and is recommended by the Parkinson Study Group⁴². The MoCA test is designed to assess executive function, higher level language abilities, memory, and complex visuospatial processing, which are areas that may be affected more commonly in PD dementia.

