6. The **Geriatric Depression Scale-Short Form** is a 15-question assessment that has been validated in older adults and is recommended as a screening test for depression in adults with PD⁴³.
7. The **Self-Efficacy for Managing Chronic Disease** questionnaire is a 6-item questionnaire developed through the Stanford Patient Education Research Center. It covers several domains that are common across many chronic diseases, symptom control, role function, emotional functioning and communicating with physicians⁴⁴.
8. **Physical Exam and Laboratory testing**
 - Urinalysis (for all participants) and pregnancy test (for women of child-bearing age). If bacteriuria is suggested by screening urinalysis⁴⁵, a culture will be sent and bacteriuria (>100K colony forming units) will be eradicated by a 7-day antibiotic course with permission/notification sent to their primary care provider. Participants will be re-assessed for UI following treatment. Participants with unexplained, persistent hematuria will be referred for an appropriate evaluation.
 - HgbA1c if the participant is diabetic and has not had an HgbA1c in the 3 months prior to enrollment.
 - Basic metabolic panel if the participant has not had an assessment in the 6 months prior to enrollment.

Enrollment and Neuropsychological Assessment:

One week later, potential participants will return for visit two. Study staff will review the completed bladder diary, questionnaires, and PVR and will determine if the participant qualifies for the study. Once enrolled, participants will undergo a brief neuropsychological battery and a motor task of procedural learning. These tests will be administered by a research assistant so that the principal investigator is blinded to baseline performance on the SRTT and cognitive function. The selected tests correspond with the battery piloted in the PI's current Rehab R&D CDA-2 study and are manageable for participants with PD. These assessments will

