Randomization: At the second visit, eligible participants will be randomized to one of two groups: treatment with PFME-based behavioral therapy or solifenacin drug therapy. Participants will be stratified by site, gender, UI severity (< or \geq a score of 9 on the ICIQ-OAB), and PD motor symptom severity (MDS-UPDRS < 33 on the part 3 motor score)⁵⁹. Participants will be randomized through computer-generated block randomization in groups of six. Based on preliminary data showing these cut points approximate the means among our randomized participants, we do not anticipate four stratification variables will present a challenge to recruitment. While participants will not be blinded to treatment group, the interventionist will be blinded to the participant's performance on the neuropsychological tests and SRTT performance.

Data Management: Participants' assessment data will be kept in a locked cabinet behind a locked door at each site of the Birmingham/Atlanta GRECC and the Richmond PADRECC. Bladder diaries will be scored by a research assistant who is blinded to the assigned treatment group. Data from the Birmingham and Richmond sites will be uploaded to a secure VA server in the form of PDF documents scanned on a VA device behind the VA firewall. Deidentified data will be entered and verified in Redcap by research staff at the Atlanta site, which will ensure accuracy of the data. A standard form will be used to record the date and reason for all

exclusions and dropouts, and these data will also be entered into the master database. Four times per year the PI will meet with the Atlanta-based data manager to review accrual, data entry, and eligibility criteria and examine the database for outliers or database entry errors at each site. The Redcap database will then be converted and data analyses will be completed in SAS 9.4 (SAS Institute, Cary, NC). Additional details regarding confidentiality of patient data are included in the Human Subjects plan.

Specific Aim #1: Using a RCT, determine non-inferiority of pelvic floor muscle exercise-based behavioral therapy versus drug therapy for urinary symptoms in PD.

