Urge suppression strategies involve teaching participants to respond adaptively to the sensation of urgency. Instead of rushing to the toilet, which increases intra-abdominal pressure and leads to visual cues that can elicit incontinence, participants will be instructed to pause, sit down, if possible, relax the entire body, and contract the pelvic floor muscles repeatedly to diminish urgency, inhibit detrusor contraction, and prevent urine loss ("freeze and squeeze"). This technique typically leads to the diminution of urgency within 1 minute. When the urgency subsides, participants are instructed to proceed to the toilet at a normal pace. Participants

with stress-related urine loss will also be instructed how to contract pelvic floor muscles immediately prior to precipitants of stress leakage (sneezing, coughing, or laughing). Other **behavioral techniques** introduced at the randomization visit for participants in the behavioral therapy group will include instruction on the management of constipation, fluid intake modification, or scheduled voiding (attempting to void on a predetermined schedule). Participants in the behavioral therapy group will maintain a 7-day bladder diary for eight weeks after randomization to mirror the behavioral intervention in the BETTUR and BETTUR2 studies.

The intervention will be initiated at the 2nd clinic visit (randomization visit). Participants will complete the Patient Global Symptom Control instrument at the 5th visit (week 6 - midpoint of study) to assess whether behavioral therapy is providing control of OAB symptoms; responses to the statement, "This treatment has given me adequate control of my overactive bladder symptoms" range from 1 (disagree strongly) to 5 (agree strongly). Participants will be offered an additional session of PFME training if they meet at least one of the following criteria: a) the participant desires further reinforcement of the pelvic floor muscle techniques, or b) the participant reports a Patient Global Symptom Control score of 1 to 3.

Drug Intervention: Solifenacin

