Participants who are randomized to drug therapy will receive solifenacin at visit 2 (randomization visit). The starting dose will be 5 mg by mouth once daily. Participants in the drug therapy group **will not receive any of the educational or exercise components of behavioral therapy**. Participants will complete a 7-day bladder diary at baseline, 6 weeks, and 12 weeks post-randomization, which will include a single 24-hour frequency volume chart at each time point. At visit 5 (week 6 – midpoint of study) solifenacin dose escalation to 10 mg will be allowed if the Patient Global Symptom Control score is 1 to 3, indicating inadequate symptom control, and the participant reports that the side effects of drug therapy are tolerable. Individual titration of drug therapy mirrors the study design from Urge PD, which was the first pilot randomized controlled trial of a bladder relaxant drug in a Parkinson's patient population^{34,63}. Additionally, individual titration of drug therapy mirrors clinical practice and the methodology for behavioral therapy implementation, which also involves individual titration of exercise-based strategies depending on symptom response. Failure to individually titrate drug therapy could bias the results of the study toward behavioral therapy. An assessment for adverse drug events will occur at each in-clinic or telephone visit after randomization using a standardized checklist. If any participant experiences adverse events after the dose increase, he/she may return to the 5mg daily dose or discontinue the medication. If the medication is discontinued, the participant will be offered the opportunity to continue the study for data collection only.

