To assess the potential impact on motor symptoms, we will assess the change in the motor symptom subscale of the MDS-UPDRS (part 3 score). Similar to the cognitive testing, baseline and 12-week post-randomization assessments will be evaluated using paired t-tests to assess for change within the drug group and two-sample t-tests for difference across groups, with the behavioral therapy group serving as a control for this analysis. Previous research suggests an increase in the MDS-UPDRS part 3 score of 4.6 points is associated with clinically relevant decline in motor function⁷⁰.

Visit Schedule

Visit 1: Baseline (One phone/telehealth session and one in-person session)

Explanation of study procedures and consent to be a participant

Interview: Demographics, continence and medical history, MoCA, LSA, GDS

Physical: Height, weight, vital signs, cardiac, pulmonary, and abdominal exam, genital and rectal exam, basic neurologic exam, MDS-UPDRS, determination of post-void residual by bladder ultrasound

Laboratory Examination: Urinalysis and BMP and HgbA1c if indicated

Education: How to complete bladder diary, handout take-home questionnaires (ICIQ-OAB and OAB-QOL)

Visit 2 (Part 1) : Randomization

Interview: Collect and review 7-day bladder diary, ICIQ questionnaires

Physical: Vital signs; review laboratory results; determination of post-void residual by bladder ultrasound if not conducted at first visit;

Procedure: **Randomization (Behavioral Therapy or Drug Therapy)**

Behavioral Therapy	Drug Therapy

Visit 2 (Part 2): Behavioral Therapy Randomization
 
Procedure: Neuropsychological battery, SRTT, Pelvic floor muscle exercise training
 
Education: specific behavioral techniques for constipation, modification of fluid intake or timed voiding
	
Visit 2 (Part 2) : Drug Therapy Randomization
 
Procedure: Neuropsychological battery, SRTT
 
Education: Medication

Visit 3: Behavioral Therapy (2 weeks)
 
Interview: Review PFME record, address new problems, reinforce practice at home and verbal feedback regarding muscle control
 
Education: Urge suppression strategy, management of stress-related urine loss (if applicable)
	
Visit 3: Drug Therapy (2 weeks)
 
Interview: Medication Management, Medication Side Effects
 
Education: Medication & Bladder Diary & Forms (to return at Visit 5)

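### The plan states no blinding to arm for the week-12 raters of the Aim 2b outcomes, which matters most for the examiner-rated MDS-UPDRS part 3

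*Combined protocol and SAP*

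**What the plan says.** The plan describes three blinds.

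- Enrollment and Neuropsychological Assessment: the tests are "administered by a research assistant so that the principal investigator is blinded to baseline performance on the SRTT and cognitive function".
- Randomization: "While participants will not be blinded to treatment group, the interventionist will be blinded"; the rest of that sentence limits the interventionist's blind to results on the neuropsychological tests and the SRTT.
- Data Management: "Bladder diaries will be scored by a research assistant who is blinded to the assigned treatment group".

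Only the third hides the arm. The first two hide scores.

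Aim 2b asks whether drug treatment, compared with exercise therapy, worsens executive function and motor severity. Its Data Analysis section compares the cognitive tests and the change in MDS-UPDRS part 3 between arms with two-sample t-tests, the behavioral arm serving as control. It cites 4.6 points on part 3 as a clinically relevant decline. Baseline assessments, item 2, describes the motor component of the MDS-UPDRS as "a physical examination of motor function by the investigator".

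Diary schedules differ by arm. Under Behavioral Intervention, participants "will maintain a 7-day bladder diary for eight weeks after randomization"; Table 7 instead marks baseline and weeks 2, 6 and 12 for that arm. Under Drug Intervention, "Participants will complete a 7-day bladder diary at baseline, 6 weeks, and 12 weeks post-randomization".

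**The concern.** Participants cannot be blinded here, so masking the assessor is the main protection left for an outcome that depends on an examiner's judgment. The plan gives that protection to the diary scorer but does not state it for the examiner of part 3 or the tester who gives the battery. An examiner who knows the arm and expects drug harm, or expects none, could score slightly differently in the two arms. That shift would add directly to the between-arm difference that answers Aim 2b. The plan says this answer should help patients and providers choose their next treatment, whatever the non-inferiority result.

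A separate and smaller issue is the diary scorer's blind. If the scorer sees each participant's whole series of diaries, the number of diaries could give the arm away.

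**Working it through.** **1. Which blinds cover the Aim 2b raters.** The plan has no stated figure to reproduce here, so the first check is textual.

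| Outcome | Rater described | Blinding to arm stated? | Room for judgment |
|---|---|---|---|
| MDS-UPDRS part 3 | The investigator | No | High |
| Wisconsin Card Sorting, Subject Ordered Pointing, other examiner-administered tests | A research assistant | No | Lower; card-sort performance is a count of perseverative errors |
| SRTT | A research assistant, times recorded by software | No | Least |
| Bladder diary (Aim 1 secondary outcomes) | A research assistant | Yes | Not an Aim 2b outcome |

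**2. Timing.**
- Part 3 is a stratification factor, so its baseline rating must precede allocation. The week-12 rating has no such protection, so a shift at week 12 enters the change score in full.
- The Visit Schedule puts the baseline neuropsychological battery in Visit 2 (Part 2), after randomization and inside the arm-specific columns. The baseline tester may therefore know the arm too.
- The Visit 7 list omits the MDS-UPDRS, although Table 7 and the Aim 2b Measures and Data Analysis text require it at 12 weeks. Neither its rater nor its place in the visit is given. The visit also includes diary review and, per Table 7, the adverse-event checklist and adherence questionnaire, any of which can disclose the arm.

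**3. Size of a rater shift on part 3 (illustration only).** Inputs:
- 40 per arm: the 80 planned completers, split equally.
- SD of the 12-week change, 6 to 8 points: assumed, not in the documents.
- Two-sided 5% test: assumed. The plan gives no alpha for Aim 2b; the one-sided 0.025 belongs to the primary test.
- Differential shift b of 1 or 2 points with no true effect: assumed.

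SE = SD × √(2/40), which is 1.342 at SD 6 and 1.789 at SD 8.

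P(reject) = Φ(b/SE − 1.96) + Φ(−b/SE − 1.96)

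| SD | b = 0 | b = 1 | b = 2 |
|---|---|---|---|
| 6 | 5% | 11.6% | 32.0% |
| 8 | 5% | 8.6% | 20.1% |

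Example, SD 6 and b = 2: 2/1.342 = 1.491; Φ(−0.469) + Φ(−3.451) = 0.320.

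Using the noncentral t over a wider assumed SD of 5 to 10, a 1-point shift gives 14.3% down to 7.3%, and a 2-point shift 42.4% down to 14.3%. Two points is 2/4.6 = 43% of the plan's clinically relevant change.

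**4. Diaries.** Whether the behavioral schedule is eight weeks of diaries or only an extra one at week 2, that arm's file holds diaries the drug arm's file lacks. Baseline, week 6 and week 12 are common to both arms in Table 7. The plan does not say which diaries reach the scorer.

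**The case against.** The strongest reply is that the plan is silent on rater blinding and does not say that raters know the arm. A reader might infer that nobody rating at week 12 is blinded. The documents do not support that: they do not say what the week-12 raters will know, and the battery is given by a research assistant who need not be involved in treatment. What stands is that no blind is stated, so following the plan as written does not secure one.

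A reader might also infer that the diary scorer's blind is already broken. That is not shown. Study documents carry only a study ID, and nothing says the scorer receives the interim behavioral diaries. The blind is at risk. Even if it failed, the diaries feed Aim 1 secondary outcomes, so the drug-harm comparison would not be affected. Nor does the plan claim objectivity for diary-reported incontinence, urgency or nocturia; it uses that word for change in mean voided volume.

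Three further limits are fair.
- The team's expectation does not clearly run one way. The Aim 2b rationale says anticholinergics reduce motor symptoms and that solifenacin is designed for less cognitive risk, and Potential Risks cites a study with no cognitive effect at 5 mg.
- Pill counts are mentioned as an adherence measure but are not tied to Visit 7, so they cannot be counted as a source of unblinding at that visit.
- The SD, the shift and the alpha in the illustration are all assumed.

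None of this supplies a masked examiner for part 3.

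**Conclusion.** The concern holds as a gap in the plan: blinding to arm is not stated for those who rate the week-12 Aim 2b outcomes. Part 3 carries most of the exposure, the examiner-administered tests less, and the SRTT least, although unblinded participants can still influence their own performance. If a differential shift of 1 to 2 points occurred, the false-positive rate would be about 9%-12% to 20%-32% under the stated assumptions. The documents give no basis for saying that such a shift will occur, or in which direction. The risk to the diary scorer's blind is a separate, lesser point about Aim 1 secondary outcomes. The primary outcome is a self-completed questionnaire and is unaffected. The gap should be closed because Aim 2b is a named specific aim and the remedy is cheap.

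**What to change.** 1. In Randomization, the Aim 2b Data Analysis and the Visit 7 list, state that part 3 and the neuropsychological battery are done by existing qualified site staff who do not deliver treatment and are not told the arm. Behavioral therapy is given by a nurse practitioner interventionist and the battery by a research assistant, so the roles can be kept apart.
2. Add the MDS-UPDRS to the Visit 7 list. Do it and the battery first, before diary review, the adverse-event checklist and the adherence questions. Ask participants not to reveal their treatment, and record any unblinding.
3. Do the baseline battery before allocation is revealed, and move it out of the arm-specific columns of the Visit Schedule.
4. If a site cannot mask its raters, say so and report it as a limitation.
5. For the diary outcomes, give the scorer only the baseline, week 6 and week 12 diaries, under study ID, for both arms. Interim behavioral diaries stay with the interventionist. Reconcile the eight-week diary text with Table 7.

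Cost: no new staff or procedures. There is some scheduling constraint, chiefly at small sites, and participants will occasionally unblind a rater.

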Power Analysis: The power analysis is informed by the ICIQ-OAB symptom score reduction observed in the BETTUR PD and BETTUR2 studies of behavioral therapy for urinary symptoms in PD. Based upon the bladder diary-derived UI frequency data (consistent measure used in both behavioral and drug trials), the effect of behavioral therapy and drug therapy to reduce UI frequency is similar. The ICIQ-OAB symptom score range is 0-16, with higher scores indicating worse symptoms. A score \geq 7 would indicate clinically significant OAB symptoms (urgency, frequency, urgency UI, nocturia) occurring on average at least *sometimes*. In our previous studies, we have observed a 2-3 point reduction in the symptom score, which represents a 12%-19% reduction from baseline^{24,64}. The minimally clinically important difference for the ICIQ-OAB is defined as a statistically significant reduction in the symptom score that is accompanied by a reduction in bother and improvement in OAB-specific QOL. Because the observed reduction **\geq 2 points** represents a statistically and clinically meaningful difference, we propose a non-inferiority margin of 15%. Thus, we will randomize 90 participants in order to complete the interventions in 80 participants, which assumes 85% power and a non-inferiority margin on the OAB symptom score of 15% at 12-weeks post-randomization. **Table 6 indicates that the proposed sample size will permit an assessment of non-inferiority within a range of potential non-inferiority margins that correspond to outcome assessments in our pilot studies.**

Standard Deviation of 12 week ICIQ-OAB Symptom Score	Margin of Non-Inferiority Between Groups at 12 weeks (Assumes OAB Symptom Score at baseline of = 8.1)				
	10%	12.5%	15%	20%	
	1.0	23	16	11	7
2.0	89	59	40	24	
3.0	198	131	88	52	

Table 7: Summary Outcome Assessments

Outcome Assessment	Baseline Visit 1/Visit 2	2 weeks Visit 3	4 weeks Visit 4	6 weeks Visit 5	8 weeks Visit 6	12 weeks Visit 7
ICIQ-OAB	X			X		X
7-day Bladder Diary (drug)	X			X		X
7-day Bladder Diary (behavioral)	X	X		X		X
7-day PFME Record (behavioral)		X				
ICIQ-OAB QOL	X			X		X
Benefit & Satisfaction				X		X
Life Space Assessment	X			X		X
Self Efficacy for Chronic Disease Management	X					X
Patient Global Symptom Control Score				X		X
Adverse Event checklist	X	X	X	X	X	X
Adherence Questionnaire		X		X		X
Neuropsychological battery	X					X
MDS-UPDRS	X					X

Data Analysis:

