Primary Outcome for Aim 1: To evaluate the impact of treatment within group, we will first use a random effects mixed model with adjustment for baseline OAB symptom severity to compare mean ICIQ-OAB symptom scores across the three time points. In order to test for non-inferiority of behavioral therapy compared to drug therapy, we will assess the difference in the mean 12-week post-randomization ICIQ-OAB symptom score between groups using a two-sample t-test, assuming a non-inferiority margin of 15% and a standard deviation of 2.0 points. The significance level of the test will be set at an α of 0.025 for a one-sided test of significance.

Secondary Outcomes: The pre-treatment and post-treatment frequency of UI based on the bladder diary will be used to calculate a percentage change for each participant ($[\text{pre-treatment frequency} - \text{post-treatment frequency}] / [\text{pre-treatment frequency}] \times 100\%$). Based on pilot study results, non-normality of the diary data is anticipated and thus the Wilcoxon rank sum test will be used for bladder diary-reported outcomes (UI, urgency, nocturia). Questionnaire-based secondary outcomes (ICIQ-OAB bother score, ICIQ-QOL, benefit and satisfaction, self-efficacy, voided volume, and the Life Space Assessment) will be assessed between groups using a t-test. Twenty-four hour voided volume measures will permit an evaluation of nocturnal urine production as a confounding factor for response to treatment among persons with nocturia. Nocturnal urine production includes the sum of all voided volumes after going to bed with the intention of sleeping and the subsequent first voided volume the next morning. Additionally, an evaluation of change in mean voided volume provides an objective measure of functional bladder capacity.

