The sample size is informed by the ICIQ-OAB symptom score reduction observed in the BETTUR PD and BETTUR2 studies of behavioral therapy for urinary symptoms in PD. Based upon the bladder diary-derived UI frequency data (consistent measure used in both behavioral and drug trials), the effect of behavioral therapy and drug therapy to reduce UI frequency is similar^{24,34}. The ICIQ-OAB symptom score range is 0-16, with higher scores indicating worse symptoms. A score ≥ 7 would indicate clinically significant OAB symptoms (urgency, frequency, urgency UI, nocturia) occurring on average at least *sometimes*. In our previous studies, we have observed a 2-3 point reduction in the symptom score, which represents a 12%-19% reduction from baseline^{24,64}. The minimally clinically important difference for the ICIQ-OAB is defined as a statistically significant reduction in the symptom score that is accompanied by a reduction in bother and improvement in OAB-specific QOL. Because the observed reduction (12%-19%) represents a statistically and clinically meaningful difference, we propose a non-inferiority margin of 15%. Thus, we will randomize 90 participants in order to complete the interventions in 80 participants, which assumes 85% power and a non-inferiority margin on the OAB symptom score of 15% at 12-weeks post-randomization.

Sources of Materials: The patients involved in this study will be seen in the Atlanta and Birmingham VAMC/GRECC Continence Clinics and the Philadelphia and Richmond PADRECCs. No tissue, blood, or urine samples will be stored during the study period as part of the protocol. For purposes of this research, baseline and treatment data will be stripped of all patient identifiers and each participant will be given a unique identifier for the study. Patient records will be stored in a locked cabinet in a locked office and will be accessible only to the Principal Investigator, Interventionist, Research Coordinator, Patient Recruiter, Site PI's ([name], [name], and [name]) and co-investigators ([name], [name], [name], [name]). Computer-based records will be maintained through the Veteran's Administration Computerized Patient Record System (CPRS), a secure network with password protection.

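### The 15% non-inferiority margin rests on a mislabelled percentage (a share of the 16-point scale called a reduction from baseline), and the primary test never states it in points

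*Combined protocol and SAP*

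**What the plan says.** The Power Analysis describes the scale: "The ICIQ-OAB symptom score range is 0-16, with higher scores indicating worse symptoms". It then reports the pilot experience: "we have observed a 2-3 point reduction in the symptom score, which represents a 12%-19% reduction from baseline". The sample-size paragraph under Human Subjects repeats that sentence and draws the margin from it: "Because the observed reduction (12%-19%) represents a statistically and clinically meaningful difference, we propose a non-inferiority margin of 15" per cent. At the same step the Power Analysis cites a reduction of at least 2 points instead, but it arrives at the same 15%.

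The sample-size table, which the text calls Table 6, heads its margin columns with a base: "Assumes OAB Symptom Score at baseline of = 8.1". Its cell for SD 2.0 and a 15% margin is 40 per group, which matches the plan for 80 completers at 85% power.

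The primary analysis for Aim 1 is a two-sample t-test on mean 12-week scores at one-sided alpha 0.025, "assuming a non-inferiority margin of 15% and a standard deviation of 2.0 points". The SD is in points and the margin is not. The statement of Specific Aim #1 and the opening paragraph of Research Design and Methods also give 15% without a base or a value in points.

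**The concern.** The margin is the threshold that decides the trial's primary conclusion. A percentage margin can be used only if the reader knows what it is a percentage of. Here the justification and the sample-size calculation use different bases under the same label.

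The 12%-19% range can be obtained only by dividing by the 16-point scale. On that base, 15% is 2.4 points. The table divides by an assumed baseline of 8.1, where 15% is 1.215 points, about half as much. The test compares means in points, so whoever programs it must convert 15% into points. The analysis section does not say how.

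The two values do not permit the same conclusion. The plan treats a 2-point reduction as clinically meaningful, and Aim 2a uses it to define success. A 1.2-point margin lies below that benchmark and a 2.4-point margin above it. The benchmark is a change within patients rather than a difference between arms, but it is the only yardstick in points that the plan offers.

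**Working it through.** **Inputs from the documents.** Scale 0-16; pilot reduction 2-3 points; assumed baseline 8.1 (sample-size table); margin 15%; SD 2.0; one-sided alpha 0.025; power 85%; 90 randomized, 80 completers, hence 40 per arm. **Assumption.** For sample size and power, a true difference of 0; the plan says only that the two treatments have similar effects on incontinence frequency.

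**1. The percentages.**
- Share of the scale: 2/16 = 12.5%, 3/16 = 18.75%. This is the printed 12%-19%.
- Share of baseline 8.1: 2/8.1 = 24.7%, 3/8.1 = 37.0%.
- For 12%-19% to be measured from baseline, the baseline would have to be about 16 (2/0.12 = 16.7; 3/0.19 = 15.8), the top of the scale.

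**2. The margin in points.** 0.15 × 8.1 = 1.215. 0.15 × 16 = 2.4. The ratio is 2.4/1.215 = 1.98.

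**3. Which margin the table used.** Per arm, n = 2 × SD² × (z_alpha + z_power)² / margin².

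| Margin (points) | One-sided alpha | Calculation | n per arm, normal | n per arm, t |
|---|---|---|---|---|
| 1.215 | 0.025 | 8 × (1.960 + 1.036)² / 1.215² = 48.7 | 49 | 50 |
| 1.215 | 0.05 | 8 × (1.645 + 1.036)² / 1.215² = 39.0 | 39 | 40 |
| 2.4 | 0.025 | 8 × (1.960 + 1.036)² / 2.4² = 12.5 | 13 | 14 |

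The printed 40 is not reproduced from all the stated inputs. It is reproduced with base 8.1 at one-sided alpha 0.05. A 16-point base reproduces no cell of the table at either alpha. The table was therefore not built on 2.4 points.

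**4. What the choice does to the decision.** With 40 per arm, SE = 2.0 × √(2/40) = 0.447 and the critical t on 78 df is 1.991. Non-inferiority is declared with the probability that a noncentral t with parameter (margin − true deficit)/SE exceeds 1.991.

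| True deficit of behavioral therapy | Margin 1.215 | Margin 2.4 |
|---|---|---|
| 1.215 points | 2.5% | 74% |
| 2 points | 0.01% | 14% |

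For the 2-point row the parameters are (1.215 − 2)/0.447 = −1.76 and (2.4 − 2)/0.447 = 0.89.

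**5. Power at the table's margin and the stated alpha.** With 40 per arm, 1.215/0.447 = 2.717, and Φ(2.717 − 1.960) = 0.775 (0.765 by noncentral t). If all 90 complete, SE = 2.0 × √(2/45) = 0.422, 1.215/0.422 = 2.88, and power is 0.82 (0.81 by noncentral t).

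**The case against.** The strongest defence is that the table names its base. Its heading ties the margins to a score of 8.1, its sample sizes cannot come from 2.4 points, and even the faulty sentence says the percentages are from baseline. No section calls the margin a percentage of the scale. This stands. A reader might infer that the margin has no base at all, or that the trial was designed around 2.4 points, and the documents support neither. What remains is that the table is a planning table. The section that defines the test does not repeat the base, and the reasoning offered for 15% works only on the other base.

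A second defence is that nobody says 15% was picked because it falls inside 12%-19%. The Power Analysis cites the 2-point reduction at that step. This is fair for that section, but the Human Subjects text makes the range its stated reason.

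A reader might also infer that the assumed baseline contradicts the Randomization section, where the ICIQ-OAB cut is 9 and "these cut points approximate the means among our randomized participants". That is too strong. The word is approximate, and if scores are whole numbers (an assumption) a split at 9 separates 8 from 9, which is close to a mean of 8.1. A base of 9 at alpha 0.025 does come close to the table's sample sizes (40-41 per arm at 15%). However, 9/8.1 = 1.11 nearly equals (1.960 + 1.036)/(1.645 + 1.036) = 1.12, so the arithmetic cannot separate a larger base from a looser alpha, and the heading prints 8.1. Nor does any passage say that the margin is rescaled to the observed baseline.

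**Conclusion.** The point holds in a limited form. The percentage behind the margin is mislabelled: 2-3 points is 12.5%-19% of the scale and 25%-37% of a baseline of 8.1. The Human Subjects rationale rests the 15% on the mislabelled range, and the primary analysis states the margin without a base or a value in points. The best reading of the plan is about 1.2 points, from the table.

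The 2.4-point reading is one that the analysis text fails to exclude. It is not one that the plan adopts. If it were used, a true 2-point deficit would pass about 14% of the time instead of 0.01%, assuming SD 2.0, 40 completers per arm and one-sided 0.025.

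A reader might also infer that writing down 1.2 points costs nothing because the table already uses it. The stated inputs do not support that. At 1.215 points and one-sided 0.025, power is about 77% with 80 completers and about 81% if all 90 complete, assuming no true difference. The printed 40 per arm matches 8.1 only at one-sided 0.05.

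This should be corrected before any between-arm data are examined, because it concerns the threshold for the primary conclusion.

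**What to change.** 1. State the margin as a fixed number of points, with its base, wherever it appears: Specific Aim #1, the opening of Research Design and Methods, the Power Analysis, the primary analysis for Aim 1, and the sample-size paragraph under Human Subjects. Suggested wording: the margin is 1.2 ICIQ-OAB points (15% of the assumed baseline of 8.1, which is 1.215) and is not rescaled to observed data. Use the same rounding in the test and in the power calculation.
2. In the Power Analysis and Human Subjects text, relabel the pilot reduction as 12.5%-19% of the 16-point scale, or 25%-37% of a baseline of 8.1.
3. Remove the argument that 15% follows from the 12%-19% range. Do not replace it with a claim that 1.2 points is about half of the 2-3 point reduction. That reduction is the change from baseline seen in behavioral-therapy pilots, so it does not measure solifenacin's effect and cannot support an effect-preservation argument. (1.2 is also 60% of 2 and 40% of 3.)
4. Restate the power at the stated alpha: about 77% with 80 completers and about 81% with 90.

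The first three changes are wording only. The fourth has a real cost: the sponsor must either accept power below 85% or enlarge the trial. Keeping 85% at 1.215 points needs 49-50 completers per arm. At the planned completion rate of 80 in 90, 100 completers means 100 × 90/80 = 112.5, or about 113 randomized instead of 90.
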